## 10 STATISTICAL METHODOLOGY

### 10.1 General

Data listings will be provided for the All Subjects Population. Summary statistics will be performed for subjects included in the relevant analysis populations (Safety/PK).

For continuous data, summary statistics will include the arithmetic mean, arithmetic standard deviation, median, minimum, maximum, and number. For log-normal data (eg, the PK

parameters: areas under the concentration-time curve [AUCs] and maximum observed plasma concentration [ $C_{max}$ ]), the geometric mean and geometric coefficient of variation (CV) will also be presented. For categorical data, frequency counts and percentages will be presented. Data listings will be provided for all subjects up to the point of withdrawal, with any subjects excluded from the relevant population highlighted. For the calculation of summary statistics unrounded data will be used.

Missing values will not be imputed.

Data analysis will be performed using SAS® Version 9.4.

Analysis Data Model (ADaM) datasets will be prepared using Clinical Data Interchange Standards Consortium (CDISC) ADaM Version 2.1, and CDISC ADaM Implementation Guide Version 1.1. Pinnacle 21 Community Validator Version 2.2.0 will be utilised to ensure compliance with CDISC standards.

Period day (day within the dosing period) will be used throughout all TFLs. It will be derived in the ADaM datasets (where applicable) and the mapping from study day to period day will be as follows.

	Dosing Period 1					Dosing Period 2					Dosing Period 3					Dosing Period 4		
Study Day	1	2	3	4	5	6	7	8	9	10	11	12	13	14	15	16	17	18
Period Day	1	2	3	4	5	1	2	3	4	5	1	2	3	4	5	1	2	3

### 10.1.1 Definition of Baseline and Change from Baseline

Baseline for each parameter is defined as the last value measured prior to last dosing, including repeat (vital signs and ECGs) and unscheduled (clinical laboratory parameters) readings (see Section 10.1.2 for definitions of repeat and unscheduled readings). For ECGs taken in triplicate, baseline will be the median of the last 3 values taken prior to last dosing.

Mean change from baseline is the mean of all individual subjects' change from baseline values. Each individual change from baseline will be calculated by subtracting the individual subject's baseline value from the value at the timepoint. The individual subject's change from baseline values will be used to calculate the mean change from baseline using a SAS procedure such as Proc Univariate.

### 10.1.2 Repeat and Unscheduled Readings

Repeat readings occur when the original vital signs or ECG result requires confirmation. Repeat readings are labelled as 'Repeat' in the listings and replace the original readings in all summaries and changes from baseline presentations and calculations. Prior to dosing, all readings taken in addition to the original reading are defined as predose repeats. Postdose repeat readings are defined as readings collected within 15 minutes of the actual time of the original reading. Where

results are taken in triplicate and repeated, the last 3 readings are used in all subsequent calculations.

With the exception of predose results described above, unscheduled readings for vital signs or ECGs are defined as readings collected >15 minutes from the actual time of the original reading. Where results are taken in triplicate, the original reading is defined as the first reading of the triplicate. All results not taken at a scheduled timepoint for other data types (eg, clinical laboratory parameters) are unscheduled. Unscheduled readings are labelled as ‘Unscheduled’ in the listings. Because unscheduled readings are not associated with any scheduled timepoint, they are excluded from all summaries (with the exception that they may be used as baseline, as stated in Section 10.1.1).

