#### **10.4.3 Vital Signs**

Vital signs values outside the clinical reference ranges will be flagged on the individual subject data listings.

The absolute values and changes from baseline in vital signs data will be listed and summarised by treatment. Figures of mean vital signs and mean change from baseline profiles will be presented by treatment.

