#### **10.4.4 Electrocardiogram**

The ECG data will be obtained directly from the 12-lead ECG traces. These data include the QT interval calculated using the QTcF, the PR and QT intervals, the QRS interval, and HR.

Where ECGs are measured in triplicate (at approximately 2-minute intervals), the median value will be used in all subsequent calculations.

Values for ECG parameters outside the clinical reference ranges will be flagged on the individual subject data listings.

The ECG data will be listed and summarised by treatment. Figures of mean ECG data and mean change from baseline profiles will be presented by treatment.

An outlier analysis will be performed including all individual postdose measurements (not the mean data), including all repeat and unscheduled readings. The frequency of subjects with a maximum increase from baseline in QTcF interval will be summarised for each treatment according to the following categories: >30, >60, and ≤30 ms. All incidences of >30 and >60 ms will be flagged on the listing. In addition, the frequency of subjects with QTcF postdose

values will be summarised for each treatment, according to the following categories: >450, >480, >500, and ≤450 ms. All incidences of >450, >480, and >500 ms will be flagged on the listing.

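### Does letting a confirmatory repeat replace the original vital-sign or ECG reading distort the safety summaries?

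*SAP*

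**What the plan says.** SAP Section 10.1.2 gives the reason for a repeat: "Repeat readings occur when the original vital signs or ECG result requires confirmation". Repeats are labelled in the listings, and they "replace the original readings in all summaries and changes from baseline presentations and calculations". The postdose window is fixed: "Postdose repeat readings are defined as readings collected within 15 minutes of the actual time of the original reading". A repeated triplicate is handled in the same way, with the second set displacing the first. Section 10.1.1 likewise allows predose repeats to supply the baseline for vital signs and ECGs.

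The outputs that depend on this are descriptive. Section 10.1 states that, for continuous data, "summary statistics will include the arithmetic mean, arithmetic standard deviation, median, minimum, maximum, and number". Section 10.4.3 adds that "The absolute values and changes from baseline in vital signs data will be listed and summarised by treatment". Section 10.4.4 summarises ECG data by treatment, but for QTcF extremes it sets its own rule: "An outlier analysis will be performed including all individual postdose measurements (not the mean data), including all repeat and unscheduled readings". Sections 10.4.3 and 10.4.4 flag out-of-range values in the listings. Section 10.4.6 plans no inference on safety data, and Sections 4 and 5 place the primary QTcF analysis in a separate SAP.

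**The concern.** Repeats are not taken at random. A reading is taken again because of its value, and a second reading tends to fall nearer the subject's own level. If the second always replaces the first, the largest and smallest values are selectively pulled in. Nothing in Section 10.1.2 restricts replacement to originals found technically faulty.

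The minimum and maximum are where a reader looks for isolated excursions, and they are what the rule moves most. Safety and tolerability of the two icosabutate doses is a secondary objective assessed only by description. QTcF has an outlier table built on all postdose readings, but vital signs have none, so a replaced blood-pressure or pulse value would be found only in the listings. If real excursions were hidden in this way, the tables would look more reassuring than the data.

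**Working it through.** The SAP gives no trigger for a repeat, no reliability and no vital-sign variability, so there is no figure of its own to reproduce. The size has to be explored under assumptions.

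**Inputs.** 32 subjects (Section 6). Assumed: single readings with total SD 1; reliability r (the share of variance that is the subject's true level) of 0.5 or 0.7; true shift on active treatment 0.5 SD; a repeat whenever the reading exceeds +1.5 or +2.5 SD; independent error in the repeat; the same rule at baseline.

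**Step 1: the right yardstick.** Shrinkage relative to the originals shows harm only if the originals are right. The expected maximum of 32 standard normal values is about 2.07.
- Originals: 0.5 + 2.07 × 1 = 2.57.
- True levels: 0.5 + 2.07 × √0.5 = 1.96, and 0.5 + 2.07 × √0.7 = 2.23.
- Originals therefore overstate the true maximum by 2.57 − 1.96 = 0.61 SD, or 2.57 − 2.23 = 0.34 SD.

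**Step 2: extremes and spread under the rule (simulation, 60,000 groups of 32).**

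| Quantity | r | True | Originals | Rule, +1.5 | Rule, +2.5 |
|---|---|---|---|---|---|
| Maximum | 0.5 | 1.96 | 2.57 | 2.28 | 2.28 |
| Maximum | 0.7 | 2.23 | 2.57 | 2.44 | 2.37 |
| SD | 0.5 | 0.70 | 0.99 | 0.89 | 0.95 |
| SD | 0.7 | 0.83 | 0.99 | 0.92 | 0.96 |

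In every row the rule lies between the originals and the truth. It reduces the overstatement and does not turn it into understatement. Among the readings that trigger a repeat, the root mean square error against the true level is 0.94 (r = 0.5) or 0.66 (r = 0.7) for originals at +1.5, and 1.30 or 0.85 at +2.5. For the repeat it is √(1 − r) = 0.71 or 0.55.

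**Step 3: the mean.** Attenuation of the shift = (1 − r) × [φ(trigger − 0.5) − φ(trigger)].
- Trigger +1.5: φ(1.0) − φ(1.5) = 0.2420 − 0.1295 = 0.1125. Times 0.5 or 0.3, this is 0.056 or 0.034, so the shift reads 0.444 or 0.466.
- Trigger +2.5: φ(2.0) − φ(2.5) = 0.0540 − 0.0175 = 0.0365. This gives 0.018 or 0.011, so the shift reads 0.482 or 0.489.

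This is a real bias of 2% to 11%. It is offset by lower variance. At r = 0.5 the root mean square error of the group mean change is √(2 × 0.5 / 32) = 0.177 with originals and about 0.17 under the rule at +1.5, bias included.

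**Step 4: the same on a blood-pressure scale.** Assumed: true mean 120 mmHg, between-subject SD 10, within-subject SD 4 to 10, repeat outside 90 to 140.
- True expected maximum: 120 + 2.07 × 10 = 140.7. Originals give 142.3 to 149.3; the rule gives 141.1 to 144.0.
- True chance that any of 32 subjects lies above 140: 1 − (1 − 0.0228)^32 = 52%. Originals show such a value in 64% to 93% of tables; the rule does so in 42% to 53%.
- A true mean change of zero stays zero. A true +5 reads 4.3 to 4.9, and a true +10 reads 8.6 to 9.7.

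**Step 5: sensitivity.** With a 0.5 SD shift, a +1.5 SD trigger means repeating about 16% of active readings, a rate that nothing in the SAP supports. At +2.5 SD the rate is 2.3%. With reliability 0.9 the maximum falls by only 0.02 to 0.08 SD.

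**Step 6: consistency of the text.** Sections 10.1.1 and 10.1.2 treat baseline and postdose repeats alike, so change from baseline compares like with like. The specific rule in Section 10.4.4 governs the QTcF outlier table. No two statements prescribe different handling for the same vital-sign or ECG summary.

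**The case for a change.** The strongest reply is that a safety table should show what was measured. The model above counts any short-lived departure from the subject's level as noise. A brief excursion that has passed by the time of the repeat may be real, and the table would then lose it. Retaining the original unless it is documented as faulty would avoid this, and would also avoid the attenuated mean, which is the one respect in which the rule adds bias.

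Part of this stands. A replaced vital-sign value appears in no summary table, the attenuation is genuine, and Section 10.1.2 does not itself name the Section 10.4.4 outlier analysis as an exception. But the reply does not show an error. The SAP says that a replaced reading needed confirmation, not that it was sound. When to repeat is commonly left to the protocol, so the number of sound readings overwritten cannot be known from this document. A postdose repeat must fall within 15 minutes, so an excursion that persists beyond that is still captured. Nothing removes originals from the listings, where out-of-range values are flagged and repeats labelled. Retaining originals has its own cost: under the same model it overstates the maximum and SD more.

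**Conclusion.** The concern does not hold. Selective re-measurement does pull in the extremes, but Section 10.1.2 is a clear, prespecified convention that applies equally to all treatments and agrees with the baseline definition. Under the assumed reliabilities of 0.5 and 0.7 it brings the tabulated maximum and SD nearer to the true values. It attenuates a 0.5 SD mean shift by 0.011 to 0.056 SD and leaves the accuracy of the mean change about the same.

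Choosing between the original and the confirmatory reading is a trade-off between noise-inflated extremes and slight attenuation, on which reasonable statisticians differ. No test, threshold or decision in this SAP rests on the summaries affected, and neither the QTcF outlier counts nor the primary QTcF analysis depends on the rule.

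The sizes rest on assumed triggers, reliability and independent repeat errors, none of which the SAP states. The judgement that the rule is a legitimate choice does not depend on them.

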## 10.2 Demographics and Subject Disposition

The demographic variables age, sex, race, ethnicity, body weight, height, and body mass index will be summarised by treatment sequence and listed. Subject disposition will be summarised by treatment sequence and listed.

## 10.3 Pharmacokinetic Assessment

### 10.3.1 Pharmacokinetic Analysis

The following PK parameters will be determined where possible, from the plasma concentrations of icosabutate, using non-compartmental methods in validated software program, Phoenix WinNonlin (Certara, Version 6.4 or later):

Parameter	Definition
AUC 0-t	area under the plasma concentration-time curve from time 0 to the time of the last observed plasma concentration (T last ), calculated using the linear trapezoidal rule for increasing concentrations and the logarithmic rule for decreasing concentrations
C max	maximum observed plasma concentration
T max	time of the maximum observed plasma concentration

Additional PK parameters may be determined where appropriate.

The Cmax for moxifloxacin will be calculated by iCardiac Technologies, Inc.

Pharmacokinetic analysis will, where possible, be carried out using actual postdose times recorded in the raw data. If actual times are missing, nominal times may be used with Sponsor’s approval.

Concentrations are used as supplied by the analytical laboratory for PK analysis. The units of concentration and resulting PK parameters, with amount or concentration in the unit, will be presented as they are received from the analytical laboratory.

Both Cmax and Tmax will be obtained directly from the plasma concentration-time profiles.

For multiple peaks, the highest postdose concentration will be reported as  $C_{\max}$ . In the case that multiple peaks are of equal magnitude, the earliest  $T_{\max}$  will be reported.

### 10.3.2 Criteria for Handling Concentrations Below the Limit of Quantification in Pharmacokinetic Analysis

- Concentration values that are below the level of quantification (BLQ) will be set to zero, with defined exceptions as follows;
  - Any embedded BLQ value (between 2 quantifiable concentrations) and BLQ values following the last quantifiable concentration in a profile will be set to missing for the purposes of PK analysis.
  - If there are late positive concentration values following 2 BLQ concentration values in the apparent terminal phase, these values will be evaluated. If these values are considered to be anomalous, they will be set to missing.
  - If an entire concentration-time profile is BLQ, the profile will be excluded from the PK analysis.
  - If a predose concentration is missing, these values may be set to zero for single dose studies and first dose of multiple dose studies with sponsor approval

#### 10.3.2.1 Anomalous Values

- If a value is considered to be anomalous due to being inconsistent with the expected PK profile, it may be appropriate to exclude this point from the PK analysis. However, the exclusion of data must have strong justification and will be documented in the raw data and study report.
- Embedded BLQ values may be considered anomalous depending on the route of administration and the characteristics of the drug.
- PK parameters associated with positive predose value(s) greater than 5% of  $C_{\max}$  may be excluded from the summary statistics of PK tables and statistical analysis at the discretion of the pharmacokineticist.

### 10.3.3 Presentation of Pharmacokinetic Data

#### 10.3.3.1 Presentation of Pharmacokinetic Plasma Drug Concentration Data

- The following rules will be applied if there are values that are BLQ or if there are missing values (e.g., no result [NR]) in a plasma concentration data series to be summarised.
- For the calculation of summary statistics, BLQ values will be set to zero.

- If an embedded BLQ value is considered anomalous within the concentration-time profile, this value will be excluded from the summary statistics.
- Where there is NR, these will be set to missing.
- If there are less than three values in the data series, only the min, max, and N will be presented. The other summary statistics will be denoted as not calculated (NC). BLQ is considered a value.
- If all the values are BLQ, then the arithmetic mean, arithmetic SD, median, min and max will be presented as zero, and the geometric mean and geometric CV% will be denoted as NC.
- If the value of the arithmetic mean or median is below the lower limit of quantification, these values will be presented as zero and the geometric mean and geometric CV% will be denoted as NC.
- Concentrations for which actual sampling time deviated  $> (5 \text{ mins} + 10\% \text{ of nominal time})$  will be excluded from summary statistics.

#### 10.3.3.2 Presentation Pharmacokinetic Parameters

- For the calculation of summary statistics of PK parameters, all NR and NC values in a data series will be set to missing.
- The  $AUC_{0-t}$  values will be set to NC if they have been calculated using fewer than three concentrations, and/or three concentrations if the last is  $C_{max}$ .

#### 10.3.4 Pharmacokinetic Statistical Methodology

No inferential statistical analysis will be performed.

PK parameters and plasma concentrations of icosabutate will be summarised by treatment and listed. Plasma concentrations will be graphically represented with an arithmetic mean plot and a concentration-time profile by subject (linear scale and semi-logarithmic scale).

### 10.4 Safety and Tolerability Assessments

#### 10.4.1 Adverse Events

A baseline sign and symptom is defined as an AE that starts after the subject has provided written informed consent and that resolves prior to the first dosing occasion, or an AE that starts prior to the first dosing occasion and does not increase in severity after dosing. A treatment-emergent AE (TEAE) is defined as an AE that occurs postdose or that is present predose and becomes more severe postdose.

All AEs will be listed. The TEAEs will be summarised by treatment, severity, and relationship to the study drug. The frequency (the number of TEAEs, the number of subjects experiencing a TEAE, and the percentage of subjects experiencing a TEAE) of TEAEs will be summarised by treatment, and by Medical Dictionary for Regulatory Activities system organ class and preferred term. The summary and frequency TEAE tables will be presented for all causalities and for those TEAEs considered related to the study treatment. Any severe or serious AEs will be tabulated. For any AEs that change severity ratings the AE will be included only once under the maximum severity rating in the summaries.

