## 6 STUDY DESIGN

This will be a Phase 1, single-centre, randomised, double-blind (except for moxifloxacin), placebo- and positive-controlled, 4-way crossover study assessing the ECG effects of therapeutic and supratherapeutic doses of icosabutate in healthy male and female subjects.

Thirty-two subjects will be randomised to 1 of 12 treatment sequences (Table 1), with approximately 3 subjects randomised into 8 of the 12 sequences, and 2 subjects randomised into 4 of the 12 sequences, and will receive a single oral dose of each of the following treatments, with a minimum 5-day wash-out between doses:

- therapeutic dose of icosabutate (600 mg)
- supratherapeutic dose of icosabutate (2000 mg)
- moxifloxacin (400 mg)
- placebo

[figure not shown]
Moxifloxacin will be used as a positive control to determine the assay sensitivity of this study, with an expected peak QT effect (placebo-corrected change-from-baseline QTcF [ $\Delta\Delta$ QTcF]) of 10 ms to 15 ms.

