**Table 1: Treatment Sequences**

Treatment Sequence	Dosing Period			
	1 (Day 1)	2 (Day 6)	3 (Day 11)	4 (Day 16)
1	icosabutate (600 mg)	icosabutate (2000 mg)	placebo	moxifloxacin (400 mg)
2	icosabutate (2000 mg)	moxifloxacin (400 mg)	icosabutate (600 mg)	placebo
3	placebo	icosabutate (600 mg)	moxifloxacin (400 mg)	icosabutate (2000 mg)
4	moxifloxacin (400 mg)	placebo	icosabutate (2000 mg)	icosabutate (600 mg)
5	icosabutate (2000 mg)	placebo	icosabutate (600 mg)	moxifloxacin (400 mg)
6	placebo	moxifloxacin (400 mg)	icosabutate (2000 mg)	icosabutate (600 mg)
7	icosabutate (600 mg)	icosabutate (2000 mg)	moxifloxacin (400 mg)	placebo
8	moxifloxacin (400 mg)	icosabutate (600 mg)	placebo	icosabutate (2000 mg)
9	placebo	icosabutate (600 mg)	icosabutate (2000 mg)	moxifloxacin (400 mg)
10	icosabutate (600 mg)	moxifloxacin (400 mg)	placebo	icosabutate (2000 mg)
11	icosabutate (2000 mg)	placebo	moxifloxacin (400 mg)	icosabutate (600 mg)
12	moxifloxacin (400 mg)	icosabutate (2000 mg)	icosabutate (600 mg)	placebo

Subjects will be screened to assess their eligibility from Day -28 to Day -2. Subjects will be admitted to the Clinical Research Unit (CRU) on Day -1 and remain in the CRU until Day 18. Each subject will participate in 4 dosing periods, with doses administered in the morning of Days 1, 6, 11, and 16 after an overnight fast of at least 8 hours (not including water). Dose administration in each dosing period will be separated by a wash-out period of at least 5 days. There will be a Follow-up Visit 7 to 10 days after the final dose administration. An overview of the study design is shown in Figure 1.

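### In this four-period crossover, does counting an adverse event once at its maximum severity file events under the wrong treatment?

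*SAP*

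**What the plan says.** All of the relevant text is in SAP Section 10.4.1, read against the design in Section 6.

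- **Definition.** "A treatment-emergent AE (TEAE) is defined as an AE that occurs postdose or that is present predose and becomes more severe postdose".
- **Pre-existing events.** A baseline sign or symptom includes "an AE that starts prior to the first dosing occasion and does not increase in severity after dosing". The anchor is the first dose of the study, not the dose of each period.
- **Tabulation.** "The TEAEs will be summarised by treatment, severity, and relationship to the study drug". Frequency tables give the number of events and the number and percentage of subjects, by treatment and coded term.
- **Severity.** "For any AEs that change severity ratings the AE will be included only once under the maximum severity rating in the summaries".
- **Listings and inference.** Every adverse event is listed (Section 10.4.1). No inferential safety analysis is planned (Section 10.4.6).
- **Design.** The trial is a "placebo- and positive-controlled, 4-way crossover study", and "Thirty-two subjects will be randomised to 1 of 12 treatment sequences" (Section 6). Below Table 1 the SAP adds: "Dose administration in each dosing period will be separated by a wash-out period of at least 5 days". Section 8 expects at least 28 completers.

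**The concern.** A rule that counts each event once at its worst grade is natural in a parallel-group trial, where a subject has only one treatment. Here each subject can contribute to all four treatment columns.

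Suppose an event is mild after treatment X, still present at the next dose, and severe after treatment Y. Read period by period, it is a TEAE of X because it began after X. It is also a TEAE of Y because it falls under the limb "or that is present predose and becomes more severe postdose". The once-only rule appears to allow one entry. Placed under X, that entry charges X with a severity reached only after Y. Placed under Y, it removes an event that began after X.

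Safety and tolerability of the 600 mg and 2000 mg doses is a secondary objective (Section 5), and these descriptive tables are its result. In the worst case, a mild event on placebo that became severe after 2000 mg would be tabulated as a severe placebo event, with nothing shown under 2000 mg. The table of severe events is the most exposed.

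**Working it through.** The SAP states no figure on this point, so there is none to reproduce. The check has three parts.

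**1. What the sentences fix.**

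| Sentence | Fixes | Leaves open |
|---|---|---|
| TEAE definition | whether an event is treatment-emergent | which dose is meant, and which treatment owns the event |
| Tabulation | that the tables are split by treatment | how an event is assigned to a treatment |
| Severity rule | the grade shown, and a single entry | whether single means per treatment or per study |

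Two readings avoid any contradiction:

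- Once per treatment. The event appears under X at the grade reached before the next dose and under Y at its later grade.
- Predose means before the first dose of the study, as in the neighbouring baseline definition. An event that starts after the Period 1 dose is then one TEAE by its first limb, whichever column it is placed in.

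A conflict arises only if the definition is applied period by period and the severity rule is applied across the whole study. The SAP states neither.

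**2. What moves in the tables.** Take the mild-then-severe event above, in a subject with no other TEAE under X or Y. The benchmark counts it under both treatments, each at its own grade.

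| Filing | TEAE incidence, X | TEAE incidence, Y | Severe row, X | Severe row, Y |
|---|---|---|---|---|
| Under both (benchmark) | 1 | 1 | 0 | 1 |
| Once, under X | 1 | 0 | 1 | 0 |
| Once, under Y | 0 | 1 | 0 | 1 |

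Overall incidence changes in one column only, whichever filing is used. Movement in opposite directions occurs only in the severe row, and only when the event is filed under X.

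**3. Size.**

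- Weight of one subject in a treatment column: 1/n. With 32 randomised, 1/32 = 3.1 percentage points. With 28 completers, 1/28 = 3.6 points. This is the weight of any single subject in any table, and not an effect of this rule.
- Opportunities: 12 sequences × 3 transitions = 36. Each of the 12 ordered treatment pairs occurs in 3 sequences (12 × 3 = 36). If all 32 subjects complete, there are 32 × 3 = 96 subject transitions. Across sequences, no ordered pair is favoured.
- Expected number affected: this cannot be computed, because the SAP gives no rate of events that persist across a dose and worsen. If 0 to 2 subjects were affected (an assumption), and all in the same column, that column would shift by 0 to 2/28 = 7.1 points.

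**The case for a change.** The strongest argument for a change is that the SAP leaves the choice to programming. Section 10.1 maps study day to period day for the crossover, yet adverse events have no period anchor. The baseline definition refers only to the first dose, so it does not settle Periods 2 to 4. Section 4 says the SAP supersedes the protocol's statistical considerations, so a protocol convention that counted the event twice would still have to be squared with the once-only wording. A listing lets a reader trace a case but does not correct a table. One or two sentences would close the gap.

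Part of this stands: the text shown does not say which treatment receives an event that spans a dose and worsens. The rest is weaker.

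- The wording does not preclude counting once per treatment.
- The table shells, which Section 4 describes as a separate document, may carry the attribution convention. The rules for recording adverse events, including whether a worsening is entered as a new event, commonly sit in the protocol. Such a recording rule is not a statistical consideration that the SAP would override. Neither document was available for this check.
- Counting the event under two treatments is one convention among several. The event totals across columns would then exceed the number of distinct events, and dated severity changes would be needed, which the SAP does not say are collected.

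**Conclusion.** No change to the plan is needed. Counting once at maximum severity is sound for any event that stays within one dosing period. For an event that crosses a dose and worsens, Section 10.4.1 leaves the attribution unstated, but it does not state a wrong one and does not contradict its own TEAE definition. Distortion of the treatment comparison has not been shown.

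What remains is a missing detail for a narrow case: an event after a single dose, in a healthy subject, that outlasts at least 5 days and then worsens after the next dose. One such subject would move one column's overall incidence by 3.1 to 3.6 percentage points, and could appear in the severe row of the wrong column under one of the possible filings. Analysts can settle this sensibly when the tables are programmed.

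This conclusion assumes that such events are few, which is plausible but not quantified in the SAP. It also relies on the tables being descriptive and on the complete listing of events, both of which the SAP states. The primary QTcF objective is not affected.
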